where  $\ln(\frac{CCI}{CCI})$  corresponds to a margin for NI, and  $\mu_1$  and  $\mu_2$  are the GMTs from Arm C and Arm D, respectively, measured at 4 weeks after vaccination.

$$H_{02}$$
:  $\pi_1 - \pi_2 \le CC$  %,

where  $\pi_1$  and  $\pi_2$  are the proportions of participants achieving seroconversion or seroresponse at 4 weeks after vaccination for Arm C and Arm D, respectively.

For evaluation of immunogenicity secondary objectives (Cohort 3), 1 statistical hypothesis for each target strain will be defined as described below:

$$H_{01}: \ln(\mu_1) - \ln(\mu_2) \le \ln(\frac{CCI}{L})$$

where  $\ln(\text{CCI})$  corresponds to a  $\frac{\text{CCI}}{\text{margin for NI}}$  margin for NI, and  $\mu_1$  and  $\mu_2$  are the GMTs in Arm E and the corresponding comparative (Arm F and Arm G) and experimental (Arm H) vaccine groups, respectively, measured 4 weeks after vaccination.

For evaluation of the immunogenicity secondary objective (Cohort 2), 2 statistical hypotheses for each targeted seasonal strain ([CCI recommended by WHO) will be defined as described below:

$$H_{01}: \ln(\mu_1) - \ln(\mu_2) \le \ln(0)$$

where  $\ln(\Box)$  corresponds to a  $\square$  margin for superiority, and  $\mu_1$  and  $\mu_2$  are the GMTs from Arm C and Arm D, respectively, measured at 4 weeks after vaccination.

$$H_{02}$$
:  $\pi_1 - \pi_2 \le \%$ ,

where  $\pi_1$  and  $\pi_2$  are the proportions of participants achieving seroconversion at 4 weeks after vaccination for Arm C and Arm D, respectively.

For each strain, NI based on GMT will be declared if the lower limit of the 2-sided 95% CI for the GMR is CO NI based on seroconversion or seroresponse (Cohort 2 only) will be declared if the lower limit of the 2-sided 95% CI for the difference in percentages of participants achieving seroconversion or seroresponse is greater than CO (Section 1) superiority (Cohort 2 only) based on GMT will be declared if the lower limit of the 2 sided 95% CI for the GMR is CO (Superiority based on seroconversion (Cohort 2 only) will be declared if the lower limit of the 2-sided 95% CI for the difference in percentages of participants achieving seroconversion is CO

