#### Model-based GMR

The model-based GMR and associated 95% CI will be calculated by exponentiating the difference in LS means and the corresponding CIs based on the analysis of logarithmically transformed assay results using a linear regression model that includes the baseline neutralizing titer, age, and vaccine group as covariates.

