## 9.3.2. Primary Endpoints/Estimands Analysis

Endpoint	Statistical Analysis Methods
Safety	
 
Descriptive statistics will be provided for each reactogenicity endpoint for each vaccine group within each cohort. Local reactions and systemic events from Day 1 through Day 7 after each vaccination (where Day 1 is the day of vaccination) will be presented by severity and cumulatively across severity levels. Descriptive summary statistics will include counts and percentage of participants with the indicated endpoint and the associated 2-sided 95% CIs based on Clopper-Pearson method.
 

	
 
AEs and SAEs will be categorized according to MedDRA terms. Counts, percentage, and associated 2-sided 95% CIs based on Clopper-Pearson method of AEs from vaccination (Day 1) through 4 weeks after vaccination, and SAEs from vaccination (Day 1) through 6 months after vaccination will be provided for each vaccine group within each cohort.
 

	The safety data are summarized within each cohort but may also be summarized descriptively across cohorts as specified in the SAP.
Immunogenicity (Cohort 2)	GMR of HAI titers for each matched seasonal strain     4 weeks after study vaccination in participants who received     BNT162b2 (Omi XBB.1.5) to those who received BNT162b2     (Omi XBB.1.5) administered concomitantly with QIV.

[figure not shown]
Endpoint	Statistical Analysis Methods				
	The difference in percentages of participants with seroconversion to the seasonal strain (CCI) at 4 weeks after study vaccination between participants who received CCI BNT162b2 (Omi XBB.1.5) and those who received BNT162b2 (Omi XBB.1.5) administered concomitantly with QIV.				
	GMR of SARS-CoV-2 Omicron (XBB.1.5)—neutralizing titers at 4 weeks after study vaccination in participants who received BNT162b2 (Omi XBB.1.5) to those who received BNT162b2 (Omi XBB.1.5) administered concomitantly with QIV.				
	The difference in percentages of participants with seroresponse to SARS-CoV-2 Omicron (XBB.1.5) strain at 4 weeks after study vaccination between participants who received BNT162b2 (Omi XBB.1.5) and those who received BNT162b2 (Omi XBB.1.5) administered concomitantly with QIV.				
	
 
GMRs and the associated 2-sided 95% CIs will be calculated using the method described in Section 9.3.1.4 Unadjusted GMRs will be the primary approach. Adjusted GMRs will also be summarized as supportive.
 
				

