# 9.3.3. Secondary Endpoints/Estimands Analysis

Endpoint	Statistical Analysis Methods
Immunogenicity (Cohort 3)	
 
GMR of HAI titers for each matched seasonal strain (CCI) at 4 weeks after vaccination for participants who received BNT162b2 (Omi XBB.1.5) to those who received QIV alone.
 
GMR of SARS-CoV-2 Omicron (XBB.1.5)—neutralizing titers at 4 weeks after vaccination for participants who received BNT162b2 (Omi XBB.1.5) to those who received BNT162b2 (Omi XBB.1.5) alone.
 

Endpoint	Statistical Analysis Methods			
	
 
GMR of HAI titers for each matched seasonal strain (CCI) at 4 weeks after vaccination for participants who received BNT162b2 (Omi XBB.1.5) to those who received alone.
 
GMRs and the associated 2-sided 95% CIs will be calculated using the method described in Section 9.3.1.4 Unadjusted GMR will be the primary approach. Adjusted GMRs will also be summarized as supportive.
 
			
Immunogenicity (Cohort 2)	GMR of HAI titers for each matched seasonal strain (CCI) at 4 weeks after study vaccination in participants who received BNT162b2 (Omi XBB.1.5) to those who received BNT162b2 (Omi XBB.1.5) administered concomitantly with QIV.			
	The difference in percentages of participants with seroconversion to the seasonal strain (CCI) at 4 weeks after study vaccination between participants who received BNT162b2 (Omi XBB.1.5) and those who received BNT162b2 (Omi XBB.1.5) administered concomitantly with QIV.			
	
 
The same analyses and estimands as the immunogenicity primary objective for HAI response.
 
			

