2.3. Study Design

This is a Phase 3, observer-blinded study to evaluate the safety, tolerability, and immunogenicity of selected when administered in combination with BNT162b2 (Omi XBB.1.5) compared to a licensed inactivated QIV administered in the deltoid opposite to that used for administration of BNT162b2 (Omi XBB.1.5) in healthy adults 18 through 64 years of age. Additionally, the study will evaluate administration of combination with BNT162b2 (Omi XBB.1.5) in comparison to standalone administration of QIV, and BNT162b2 (Omi XBB.1.5). The vaccine candidates are divided into cohorts, where approximately 8550 total participants 18 through 64 years of age will be enrolled into 1 of 3 cohorts:

Cohort 1: Approximately 450 participants randomized in a 2:1 ratio by site-based randomization to 1 of the following:

- Arm A: CCI BNT162b2 (Omi XBB.1.5) administered in the right deltoid and placebo administered in the left deltoid, concurrently.
- Arm B: 30 μg BNT162b2 (Omi XBB.1.5) administered in the right deltoid and licensed QIV (CCI administered in the left deltoid, concurrently.

Enrollment of Cohort 1 will be paused in the IRT system after the randomization of approximately 450 participants into Cohort 1. Safety data (including e-diary data, SAEs, AEs, and AESIs) of approximately 450 vaccinated participants will be evaluated by the EDMC after 60 days

Cohort 2: Approximately 4500 participants randomized in a 2:1 ratio by site-based randomization to 1 of the following:

- Arm C: CCI /BNT162b2 (Omi XBB.1.5) administered in the right deltoid and placebo administered in the left deltoid, concurrently.
- Arm D: 30 μg BNT162b2 (Omi XBB.1.5) administered in the right deltoid and licensed QIV

Cohort 3: Approximately 3600 participants 18 through 64 years of age will be enrolled and randomized in a 2:2:1:1 ratio by site-based randomization to 1 of the following:

- Arm E: CCI /BNT162b2 (Omi XBB.1.5) administered in the right deltoid.
- Arm F: 30 μg BNT162b2 (Omi XBB.1.5) administered in the right deltoid.
- Arm G: licensed QIV CCI administered in the right deltoid.
- Arm H: CCl administered in the right deltoid.

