5.1.1. Multiplicity Adjustment

Hypothesis testing of the objectives for Cohort 2 (2 immunogenicity primary objectives and the fourth secondary objective) will be evaluated independently from that of Cohort 3 (3 immunogenicity secondary objectives) without applying any multiplicity adjustment.

Within Cohort 2, the immunogenicity primary objectives and the fourth secondary objective will be evaluated sequentially. The immunogenicity primary endpoints/estimands are considered coprimary. There are hypothesis tests (CCI) for XBB.1.5] for the immunogenicity primary NI objectives (CCI) for XBB.1.5] ws BNT162b2 [Omi XBB.1.5] administered concomitantly with QIV), with 2 statistical hypotheses for each of the targeted influenza and SARS-CoV-2 strains. Each hypothesis will be tested at a 1-sided alpha level of 0.025. The immunogenicity primary objectives will be achieved if NI is met for all statistical hypotheses. After the immunogenicity primary NI objectives (Cohort 2) are established, the statistical hypotheses for the fourth secondary objective (Cohort 2) will be tested sequentially in the following order of seasonal influenza strains:

CCI and the hypothesis will be tested first based on GMR and then based on the seroconversion rate for each strain. Therefore, the overall type I error rate within Cohort 2 is fully controlled.

Within Cohort 3, the 3 immunogenicity secondary objectives will be evaluated sequentially in the following order: comparing CCI /BNT162b2 (Omi XBB.1.5) with QIV for targeted influenza strains, CCI BNT162b2 (Omi XBB.1.5) with BNT162b2 (Omi XBB.1.5) for the SARS-CoV-2 Omi XBB.1.5 strain, and CCI /BNT162b2 (Omi XBB.1.5) with CCI for targeted influenza strains. There are hypothesis tests for the immunogenicity secondary NI objectives (CCI /BNT162b2 [Omi XBB.1.5] vs QIV for targeted influenza strains, 1 for CCI /BNT162b2 [Omi XBB.1.5] vs BNT162b2 [Omi XBB.1.5] for the SARS-CoV-2 Omi XBB.1.5 strain, and CCI /BNT162b2 [Omi XBB.1.5] vs CCI for targeted influenza strains). Each hypothesis will be tested at a 1-sided alpha level of 0.025. For objectives involving hypotheses for influenza strains, all hypotheses within the objective must be established before assessing the next objective in the sequence. Therefore, the overall type I error within Cohort 3 is fully controlled.

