5.2.2.2. Geometric Mean Ratio

Unadjusted GMR

The unadjusted GMR will be calculated as the difference in the means of logarithmically transformed assay results between 2 vaccine groups and exponentiating the difference. The 2-sided 95% CI will be obtained by exponentiating the limits of the CI for the mean difference of the logarithmically transformed assay results based on the t distribution.

Model-based GMR

The model-based GMR and associated 95% CI will be calculated by exponentiating the difference in LS means and the corresponding CIs based on the analysis of logarithmically transformed assay results using a linear regression model that includes the baseline assay results (HAI titer/SARS-CoV-2 NT), age, and vaccine group as covariates.

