6.1.2. Primary Immunogenicity Endpoints

6.1.2.1. Main Analysis

- Estimand(s) in Cohort 2:
 - GMR of HAI titers at 4 weeks after vaccination in participants who received BNT162b2 (Omi XBB.1.5) to those who received QIV administered concomitantly with BNT162b2 (Omi XBB.1.5).
 - The difference in percentage of participants with seroconversion to the seasonal strain at 4 weeks after vaccination between participants who received CCI BNT162b2 (Omi XBB.1.5) and those who received QIV administered concomitantly with BNT162b2 (Omi XBB.1.5).
 - GMR of SARS-CoV-2 (Omi XBB.1.5)—neutralizing titers at 4 weeks after vaccination in participants who received BNT162b2 (Omi XBB.1.5) to those who received BNT162b2 (Omi XBB.1.5) administered concomitantly with QIV.
 - The difference in percentage of participants with seroresponse to the SARS-CoV-2
 (Omi XBB.1.5) strain at 4 weeks after vaccination between participants who received
 BNT162b2 (Omi XBB.1.5) and those who received BNT162b2 (Omi XBB.1.5)
 administered concomitantly with QIV.
- Analysis set(s): Evaluable immunogenicity population and mITT immunogenicity population (as applicable) (Section 4).
- Analysis time point(s): 4 Weeks after vaccination.
- Statistical method(s): Analysis will be performed within each cohort independently. The unadjusted GMR and the associated 2-sided 95% CIs will be provided using methods described in Section 5.2.2.2. The difference in percentage of participants with seroconversion/seroresponse, and the associated 2-sided 95% CIs, will be calculated using the Miettinen and Nurminen method (Section 5.2.1). Seroconversion is defined as having an HAI titer <1:10 prior to vaccination and ≥1:40 at the postvaccination time point of interest, or an HAI titer of ≥1:10 prior to vaccination with a minimum 4-fold rise at the postvaccination time point of interest. Seroresponse is defined as achieving a ≥4-fold rise from baseline (before the study vaccination). If the baseline measurement is

below the LLOQ, the postvaccination measure of \geq 4 × LLOQ will be considered seroresponse. NI based on the GMR will be established if the lower bound of the 2-sided 95% CI for the GMR is greater than colored and NI based on the seroconversion/seroresponse rate difference will be established if the lower bound of the 2-sided 95% CI for the difference in percentage is greater than colored.

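### The decisive GMR tests use an unadjusted interval although the SAP already defines a baseline-and-age model for the same ratio: avoidable loss of precision, clearest in the Cohort 3 HAI comparisons

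*Protocol*

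**What the plan says.** Protocol 9.3.2 (Cohort 2 primary objectives) states: "Unadjusted GMRs will be the primary approach. Adjusted GMRs will also be summarized as supportive". Protocol 9.3.3 repeats this for Cohort 3: "Unadjusted GMR will be the primary approach". It gives Cohort 2 superiority the same analyses and estimands as the primary HAI objective. SAP 6.1.2.1 agrees: the "unadjusted GMR and the associated 2-sided 95% CIs will be provided using methods described in Section 5.2.2.2"; SAP 6.2.1 does the same for the secondary endpoints. The unadjusted interval is a two-group t interval for the difference in mean log titre.

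SAP 5.2.2.2 also defines a model-based GMR from a "linear regression model that includes the baseline assay results (HAI titer/SARS-CoV-2 NT), age, and vaccine group as covariates". Protocol 9.3.1.4 describes "a linear regression model that includes the baseline neutralizing titer, age, and vaccine group as covariates" and does not name HAI. The protocol commits to reporting adjusted GMRs as supportive; SAP 6.1.2.2 and 6.2.2 make them optional, while SAP 2.1 reports no modification to the protocol's analysis plan.

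On the structure of the Cohort 3 tests, protocol 9.1 says: "For evaluation of immunogenicity secondary objectives (Cohort 3), 1 statistical hypothesis for each target strain will be defined as described below". That hypothesis concerns the GMR only. Under SAP 5.1.1 the comparison with QIV comes first, and for the influenza objectives "all hypotheses within the objective must be established before assessing the next objective in the sequence".

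**The concern.** Titres after vaccination usually depend on titres before it, and a pre-vaccination sample is planned for every participant (protocol 8.10.1). A two-group t interval leaves that explained variation in the error term, so it is wider than necessary whenever baseline titre or age predicts the 4-week titre. The plan already contains the model that would remove it, but gives that model only a supportive place. I found no reason for this ranking in the readable text.

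The Cohort 3 HAI comparisons have most to gain. They are the smallest of the decisive comparisons, and they rest on the GMR alone, so no seroconversion test limits the gain. The QIV comparison also gates the rest: one strain that narrowly fails stops formal testing of the SARS-CoV-2 and standalone influenza comparisons. Those later comparisons address the interference question for which Amendment 2 added the cohort.

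**Working it through.** **Plan's own figures.** The assumed GMRs, evaluable numbers and power in protocol Tables 6 and 7 are redacted, so no stated power can be reproduced or called wrong.

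**Inputs from the documents.**
- Cohort 3, SAP 2.3: "Approximately 3600 participants 18 through 64 years of age will be enrolled and randomized in a 2:2:1:1 ratio", hence 1200/1200/600/600 in Arms E/F/G/H.
- Cohort 2, protocol 9.5.1: an HAI subset of 2000 v 1000; all enrolled participants (3000 v 1500) are tested for SARS-CoV-2.
- One-sided alpha 0.025 (SAP 5.1.1).

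**Assumptions.**
- 90% evaluable; all Cohort 3 participants in the relevant arms HAI-tested.
- SD of ln titre 1.2 (1.0 and 1.3 as checks).
- Noninferiority margin 1.5-fold (1.25-fold, 2-fold and a bound written as 0.67 as alternatives); superiority bound 1.0.
- R, the multiple correlation of the 4-week log titre with baseline titre and age: 0.2 to 0.7.

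**Which comparison is least precise.** At full enrolment, SE/SD = sqrt(1/n1 + 1/n2):
- Cohort 3 HAI (1200 v 600): 0.0500
- Cohort 3 SARS-CoV-2 (1200 v 1200): 0.0408
- Cohort 2 HAI (2000 v 1000): 0.0387
- Cohort 2 SARS-CoV-2 (3000 v 1500): 0.0316

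**Precision gain.** The adjusted SE is the unadjusted SE times sqrt(1 - R²), and the equivalent gain in sample size is 1/(1 - R²) - 1.

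| R | SE reduction | Equivalent extra participants |
|---|---|---|
| 0.2 | 2.0% | 4.2% |
| 0.3 | 4.6% | 9.9% |
| 0.4 | 8.3% | 19.0% |
| 0.7 | 28.6% | 96.1% |

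**Power per strain.** SE = SD × sqrt(1 - R²) × sqrt(1/n1 + 1/n2); power = Φ((ln GMR - ln bound)/SE - 1.96). Worked case, Cohort 3 HAI, R = 0: SE = 1.2 × sqrt(1/1080 + 1/540) = 0.0632; ln 0.80 - ln(1/1.5) = 0.1823; 0.1823/0.0632 - 1.96 ≈ 0.92, so power is 82.2%.

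| Case (SD 1.2) | R = 0 | 0.2 | 0.3 | 0.4 | 0.7 |
|---|---|---|---|---|---|
| Cohort 3 HAI, 1.5-fold, GMR 0.80 | 82.2 | 83.7 | 85.6 | 88.2 | 98.1 |
| Same, GMR 0.85 | 97.0 | 97.5 | 98.1 | 98.7 | 100 |
| Same, GMR 0.90 | 99.7 | 99.8 | 99.9 | 99.9 | 100 |
| Cohort 3 HAI, bound 0.67, GMR 0.80 | 80.1 | 81.6 | 83.6 | 86.4 | 97.5 |
| Cohort 3 HAI, 1.25-fold, GMR 0.95 | 77.6 | 79.2 | 81.3 | 84.2 | 96.7 |
| Cohort 3 HAI, 2-fold, GMR 0.80 | 100 | 100 | 100 | 100 | 100 |
| Cohort 2 superiority (1800 v 900), GMR 1.10 | 49.4 | 51.0 | 53.2 | 56.5 | 77.8 |
| Same, GMR 1.15 | 81.4 | 82.9 | 84.9 | 87.5 | 97.9 |
| Cohort 2 HAI noninferiority, GMR part, 1.5-fold, GMR 0.80 | 96.1 | 96.7 | 97.4 | 98.2 | 99.9 |

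For the first row with SD 1.0, power runs from 93.3 (R = 0) to 99.8 (R = 0.7); with SD 1.3, from 75.8 to 96.1. The number of strains is redacted, so joint power is not given.

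**Validity of both methods.** In a simulation of 1200 v 600 with 4000 runs per setting (no dropout, assumed bound 0.667), rejection at the margin was 2.3-2.8% unadjusted and 2.5-3.1% adjusted, with a Monte Carlo SE of about 0.25 points. With zero correlation, adjustment cost essentially nothing.

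**The case against.** The plan is not in error here. Amendment 2 introduced both GMR versions deliberately, the two documents rank the unadjusted one first throughout, and its interval is valid under randomisation. The estimand and type I error are sound, and the adjusted estimate already appears as supportive. All of this stands, and it makes the point one of efficiency only.

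The documents also cannot show that the gain matters. Margin, SD, R and evaluable fraction are all assumed, and the largest gains need R near 0.7, which nothing in the documents supports. With a 1.5-fold margin, power is already 97% at GMR 0.85. This stands too, and limits the claim to a true GMR near the margin.

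Three stronger readings are tempting but unsupported:
- *The unadjusted tests are biased or Cohort 3 is underpowered.* Randomisation secures validity, and the power tables are redacted, so inadequacy cannot be shown.
- *The influenza B results in protocol 2.2.3.2 show that the problem will arise.* They come from a different study and are given without a GMR or interval. They make a weak strain plausible and no more.
- *The wording differences between protocol and SAP alter a decision.* They concern only the supportive analysis, and SAP 5.2.2.2 already names HAI.

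For Cohort 2 noninferiority the gain is small in any case: every strain must also pass seroconversion or seroresponse, which this change does not touch and which may be the limiting test for a weak strain.

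**Conclusion.** The point holds as an avoidable loss of precision. The unadjusted GMR decides Cohort 2 noninferiority and superiority and Cohort 3 noninferiority, while a model for the same ratio, using data already collected, stands beside it as supportive. For any nonzero R the direction of the loss is certain; its size is not known from the documents. Under the stated assumptions the gain in Cohort 3 HAI power at GMR 0.80 is about 1.5-3.5 points per strain at R 0.2-0.3 and 6-16 points at R 0.4-0.7, and it is close to nil once the true GMR is well clear of the margin. The change is worth making because it needs no participants or samples. It is not needed for the trial to be valid.

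**What to change.** Before unblinded immunogenicity data are available for the affected cohort (analyses run cohort by cohort), make the SAP 5.2.2.2 model the primary GMR analysis in Cohorts 2 and 3. The covariates are the log baseline titre of the same assay and strain, age and vaccine group. Keep the unadjusted GMR as supportive.

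State one rule for missing baselines, for example the pooled mean plus a missing indicator, because the evaluable set in SAP 4 requires only a valid 4-week result. Confirm that baselines below the LLOQ enter the model at half the LLOQ, as SAP 5.3 does for GMTs.

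- **Cohort 2:** change noninferiority and superiority together, by protocol amendment (with IRB/EC approval) and SAP revision. Protocol 9.3.3 ties superiority to the primary HAI analysis, and protocol 9 requires an amendment for major changes to the primary analyses. Moving superiority alone would test the same arms and strain by two methods within one sequence.
- **Cohort 3 only:** by its wording, protocol 9 may allow this through a SAP revision listed in SAP 2.1. The SAP should then acknowledge that the lead HAI GMR method differs between cohorts.
- **Either way:** align protocol 9.3.1.4 with the SAP so that HAI is adjusted for baseline HAI. If the unadjusted GMR stays primary in any cohort, reconcile the protocol's firm commitment to report adjusted GMRs with the SAP's optional wording.

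The cost is document revision and the missing-baseline rule, which the unadjusted GMR does not need.

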# 9.3.3. Secondary Endpoints/Estimands Analysis

Endpoint	Statistical Analysis Methods
Immunogenicity (Cohort 3)	
 
GMR of HAI titers for each matched seasonal strain (CCI) at 4 weeks after vaccination for participants who received BNT162b2 (Omi XBB.1.5) to those who received QIV alone.
 
GMR of SARS-CoV-2 Omicron (XBB.1.5)—neutralizing titers at 4 weeks after vaccination for participants who received BNT162b2 (Omi XBB.1.5) to those who received BNT162b2 (Omi XBB.1.5) alone.
 

Endpoint	Statistical Analysis Methods			
	
 
GMR of HAI titers for each matched seasonal strain (CCI) at 4 weeks after vaccination for participants who received BNT162b2 (Omi XBB.1.5) to those who received alone.
 
GMRs and the associated 2-sided 95% CIs will be calculated using the method described in Section 9.3.1.4 Unadjusted GMR will be the primary approach. Adjusted GMRs will also be summarized as supportive.
 
			
Immunogenicity (Cohort 2)	GMR of HAI titers for each matched seasonal strain (CCI) at 4 weeks after study vaccination in participants who received BNT162b2 (Omi XBB.1.5) to those who received BNT162b2 (Omi XBB.1.5) administered concomitantly with QIV.			
	The difference in percentages of participants with seroconversion to the seasonal strain (CCI) at 4 weeks after study vaccination between participants who received BNT162b2 (Omi XBB.1.5) and those who received BNT162b2 (Omi XBB.1.5) administered concomitantly with QIV.			
	
 
The same analyses and estimands as the immunogenicity primary objective for HAI response.
 
			

